10.3.1 Time to ADT Therapy

Time to initiation of ADT is defined as the time elapsed between study enrollment and initiation of ADT for metastatic prostate cancer.

10.3.2 Rate of Undetectable PSA

The rate of undetectable PSA is defined as the proportion of patients ever treated with prostatectomy whose PSA remains ≤ 0.2 ng/mL after 6 and 12 months following completion of treatment (salvage \pm adjuvant).

10.3.3 Safety

Routine safety and tolerability will be evaluated from the results of reported signs and symptoms, scheduled physical examinations, vital sign measurements, and clinical laboratory test results. More frequent safety evaluations may be performed if clinically indicated or at the discretion of the investigator.

Physical Examination

Complete and symptom-directed physical examinations will be performed by a licensed physician (or physician's assistant or nurse practitioner).

Vital Signs

Vital signs include blood pressure, respiratory rate, pulse rate and temperature.

Safety Laboratory Determinations

Laboratory evaluations will be performed as noted in the flow chart.

11 STATISTICAL CONSIDERATIONS

11.1 Sample size determination

The planned sample size is N = 20 evaluable subjects. The primary outcome variable of reduction in PSA $\geq 50\%$ at 6 months will be analyzed descriptively via 90% and 95% exact binomial confidence intervals. No hypothesis test will be performed on the primary outcome

variables. The sample size is justified by the width of the 95% confidence intervals. We anticipate that the PSA 50% response rate at 6 months will be 30% based on the results published by Siriwardana, as their PSA response at 6 weeks and 12 months was 43% and 23% respectively. However, the definition used here is somewhat different than the definition in that clinical study. If the observed PSA 50% response rate is 30% (6/20), the 95% exact binomial confidence interval (Clopper-Pearson) will be 12% to 54 %. With 20 evaluable subjects the maximum width of a 95% exact binomial confidence interval is 46% (27% to 73%) and occurs when the observed response rate is 50% (10/20).

11.2 Population for analyses

11.2.1 Evaluable for safety

Patients receiving any amount of treatment or any invasive procedure/surgery will be evaluable for safety.

11.2.2 Evaluable for response

Patients are only evaluable if they complete their designated intervention:

- Patients on Arm A must complete at least 70% of planned radiation treatments;
- Patients on Arm B must complete surgery;
- Patients on Arm C must complete surgery and at least 70% of planned radiation treatments.

Patients that are unevaluable for response will be replaced.

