Recently two clinical trials have demonstrated substantial clinical benefit for early, intense treatment for subjects with metastatic hormone sensitive prostate cancer using a combination of ADT plus abiraterone (NCT00268476, NCT01715285). Intensive treatment with combination ADT and chemotherapy (NCT00309985) has similarly been demonstrated to improve clinical outcomes in subjects with metastatic hormone sensitive prostate cancer. Additionally, early treatment in patients with non-metastatic castration-resistant prostate cancer with either enzalutamide⁵ or apalutamide⁶ compared with placebo both demonstrated a significant improvement to metastasis-free survival and a similar trend for improved overall survival. This body of evidence strongly suggests that early, intense therapy may provide significant clinical benefit in subjects with hormone sensitive oligometastatic prostate cancer.

We hypothesize that local salvage treatment of oligometastatic disease identified on advanced imaging will result in long-term disease control, including optimal PSA responses and prolongation of radiographic progression-free survival. These results might translate into some men obtaining a cure of their prostate cancer, though this will have to be validated in future studies and with longer clinical follow up. Given that there is no standard of care for this setting, this clinical trial is designed to establish a standard reference for this population that can be used as the basis for additional clinical investigations in the future.

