4 STUDY DESIGN

4.1 Description

This is a Phase II non-randomized pilot study meant to establish preliminary reference response rate and duration of response for subjects with recurrent prostate cancer treated with salvage oligometastasectomy and/or radiotherapy. Treatment decisions will be based on molecular imaging (e.g., fluciclovine PET/CT or PSMA PET/CT scan or other per PI discretion): subjects with nodal disease only will be treated with oligometastasectomy, subjects with bone disease only will be treated with SBRT, and subjects with a combination of nodal and bone disease will receive both treatment. Response rates and durations will be based on PSA and imaging.

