6.4 Duration of Therapy

6.4.1 Criteria for the Discontinuation of Treatment (“Off Treatment”)

Patients may withdraw from treatment or the study overall at any time at their own request, or they may be withdrawn at the discretion of the Investigator for safety, behavioral reasons, or the inability of the patient to comply with the protocol-required schedule of study visits or procedures.

In addition to the drug-specific discontinuation criteria listed in Dose Modification Section, the following will result in treatment discontinuation:

- Adverse events or intercurrent illness that in the opinion of the investigator warrants the subject's withdrawal from study treatment

- The subject or legally authorized representative requests to discontinue the study treatment and/or study procedures
- Salvage treatment failure defined as radiographic progression per PCWG3 criteria OR RECIST 1.1. Patients taken off treatment for treatment failure will continue to be followed for toxicity assessments only every 6 months.
- Failure to initiate adjuvant radiotherapy within 4 months of completion of salvage therapy (oligometastasectomy and/or bone radiotherapy).
- Patient refused further treatment
- Significant noncompliance with the protocol schedule or treatment administration in the opinion of the investigator
- Clinical deterioration that, in the opinion of the investigator, increases the risk to the subject

Surgery may be aborted if unforeseen complications arise.

Radiation therapy courses may be shortened in case of RTOG Grade III-IV or persistent (≥ 2 weeks) Grade II toxicities. Continuation of treatment during Grade III toxicities may be allowed if the patient is benefiting as assessed by the treating investigator.

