7.1 Dose Modifications and Guidelines for Adverse Event Management for Radiotherapy

7.1.1 Dose Modifications

In the event of a clinically significant CTCAE v5 adverse event \geq grade 3, which is felt to be at least possibly related to radiation therapy, treatment will be discontinued. Treatment related adverse events \leq grade 2 may result in a reduction in the dose of radiation therapy if the treating physician feels that further radiation would be likely to exacerbate harm to the patient.

Radiation therapy courses may be shortened in case of RTOG Grade III-IV or persistent (\geq 2 weeks) Grade II toxicities. Continuation of treatment during Grade III toxicities may be allowed if the patient is benefiting as assessed by the treating investigator.

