11.3 Statistical Hypotheses and Analyses

This study is establishing baseline data for patients who have no defined standard of care therapy. All study data will use descriptive statistics and will be exploratory only.

Since this study is not using any hormonal therapy, we expect that using PSA analysis will be accurate and provide an early readout regarding the potential efficacy and clinical utility of this approach.

Primary Objective

The primary endpoint is the proportion of subjects with a reduction in PSA $\geq 50\%$ 6 months after completion of all treatment (salvage and adjuvant therapy). The observed proportion and a 95% exact binomial confidence interval will be reported for the entire group of evaluable patients (Arms A, B and C together) as well as for each cohort separately.

Secondary Objectives

1. 95% exact confidence intervals will be reported for the observed proportions with reductions in PSA $\geq 50\%$ 12 months after and $\geq 90\%$ 6 and 12 months after completion of all treatment (salvage and adjuvant therapy). This will be done for the entire group of evaluable patients (Arms A, B and C together) as well as for each Arm separately.
2. The proportion of subjects without PSA progression (defined using Prostate Cancer Working Group 3 Criteria PCWG3), will be evaluated every 3 months for 3 years after completion of all treatment (salvage and adjuvant therapy) and analyzed using Kaplan-

Meier methodology. This will be done for the entire group of evaluable patients (Arms A, B and C together) as well as for each Arm separately.

3. The time from study enrollment until the date of confirmed radiographic disease progression as defined by RECIST 1.1 and PCWG3 will be analyzed using Kaplan-Meier methods. This will be done for the entire group of evaluable patients (Arms A, B and C together) as well as for each Arm separately.
4. The time from study enrollment to the initiation of ADT will be analyzed using Kaplan-Meier methods. This will be done for the entire group of evaluable patients (Arms A, B and C together) as well as for each Arm separately.
5. The proportion of patients with a PSA ≤ 0.2 ng/mL will be evaluated 6 and 12 months after completion of all treatment (salvage and adjuvant therapy) in the subset of patients who have previously undergone prostatectomy. This will be done for the entire group of evaluable patients (Arms A, B and C together) as well as for each Arm separately.

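### Response is reported only in subjects who complete their intervention, with the rest replaced and no all-treated rate planned; the count of 20 subjects also needs consistent wording

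*Combined protocol and SAP*

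**What the plan says.** Section 11.2.2 defines the response set: "Patients are only evaluable if they complete their designated intervention". In Arm A that means 70% or more of the planned radiation, in Arm B surgery, and in Arm C both. It then adds: "Patients that are unevaluable for response will be replaced".

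For the primary endpoint, section 11.3 states: "The observed proportion and a 95% exact binomial confidence interval will be reported for the entire group of evaluable patients". The PSA secondary endpoints, the time-to-event endpoints and the quality-of-life summaries use the same set, overall and by arm. The broader set in 11.2.1 is used only to tabulate adverse events.

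The purpose is given in two places. Section 2 describes a trial "designed to establish a standard reference for this population that can be used as the basis for additional clinical investigations", and section 4.1 a study "meant to establish preliminary reference response rate and duration of response for subjects with recurrent prostate cancer".

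On numbers, 4.2 gives 20 as the total to be enrolled and the synopsis row for number of subjects gives 20. Section 11.1 and the synopsis statistics text give 20 evaluable.

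**The concern.** A completers-only rate describes subjects in whom the strategy could be delivered. A later trial that counts everyone who starts treatment needs the corresponding all-treated rate, and this plan does not estimate it.

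The protocol itself foresees treated subjects who do not complete. Section 6.4.1 says: "Surgery may be aborted if unforeseen complications arise". It also lists adverse events, refusal, clinical deterioration and radiographic progression as reasons to stop treatment. Some of these may be related to outcome. If such subjects respond less often than completers, replacing them raises the reported rate. With no hypothesis test planned, the estimate and its denominator are the study's main product.

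The mismatch in subject counts is a separate and smaller matter. Enrolling 20 and having 20 evaluable are the same only if nobody is unevaluable.

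**Working it through.** **Inputs.** From 11.1: 20 evaluable subjects, anticipated response 30% (6/20), 95% Clopper-Pearson intervals. From 11.2.2: the completion rule and replacement. From 6.1.1: bone radiation commonly in 1 to 6 fractions. The number replaced, k, is not in the documents; I assume 0 to 5.

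**The plan's own figures.** For x responders among n, the limits are the 0.025 quantile of Beta(x, n − x + 1) and the 0.975 quantile of Beta(x + 1, n − x).
- 6/20: 11.9% to 54.3%, width 42.4 points (plan: 12% to 54%).
- 10/20: 27.2% to 72.8%, width 45.6 points, the maximum over all x (plan: 27% to 73%, width 46%).

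Both reproduce, and both assume exactly 20 evaluable.

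**All-treated rate if no replaced subject responds**, 6/(20 + k):

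| k | Rate | 95% interval | Shift (points) |
|---|---|---|---|
| 0 | 6/20 = 30.0% | 11.9 to 54.3% | 0 |
| 1 | 6/21 = 28.6% | 11.3 to 52.2% | 1.4 |
| 2 | 6/22 = 27.3% | 10.7 to 50.2% | 2.7 |
| 3 | 6/23 = 26.1% | 10.2 to 48.4% | 3.9 |
| 4 | 6/24 = 25.0% | 9.8 to 46.7% | 5.0 |
| 5 | 6/25 = 24.0% | 9.4 to 45.1% | 6.0 |

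**If replaced subjects respond at rate r**, the expected rate is (6 + k·r)/(20 + k).
- r = 0.15 (assumed), k = 5: (6 + 0.75)/25 = 27.0%, a shift of 3.0 points.
- r = 0.30, k = 5: (6 + 1.5)/25 = 30.0%, no shift; the same holds for every k.

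**By arm** the shift can be larger. If an arm had 2 responders among 5 (assumed), one replaced non-responder would turn 2/5 = 40% into 2/6 = 33%.

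**How much room the 70% rule leaves**, for a single course:
- 1 fraction: it must be given.
- 2 fractions: 1/2 = 50% fails, so both are needed.
- 3 fractions: 2/3 = 66.7% fails, so all three are needed.
- 4 fractions: 3/4 = 75% passes, 2/4 = 50% fails.
- 5 fractions: 4/5 = 80% passes, 3/5 = 60% fails.
- 6 fractions: 5/6 = 83.3% passes, 4/6 = 66.7% fails.

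So with 1 to 3 fractions none may be missed, and with 4 to 6 only one.

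**Stopping for toxicity.** For a clinically significant CTCAE event of grade 3 or higher "which is felt to be at least possibly related to radiation therapy, treatment will be discontinued", according to 7.1.1. The same section says "Continuation of treatment during Grade III toxicities may be allowed if the patient is benefiting as assessed by the treating investigator". These statements must be reconciled. As they stand, they do not show how often radiation would be cut short.

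**Subjects with no 6-month PSA.** Under 6.4.1, subjects with radiographic failure are followed for toxicity only. Under 6.4.2, new anti-cancer therapy or loss to follow-up takes a subject off study. Section 11.3 does not say how either group enters the rate. They are not in the table above, because their number is unknown.

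**The case against.** The strongest reply has four parts.

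**A reader could compute the rate.** Responders come from the primary analysis and treated subjects from the safety table, both by arm. That is nearly true, but it does not make the rate a planned estimate with an interval. The division would also depend on how the safety set's reference to invasive procedures is read: screening can include a TRUS biopsy, although adverse event collection starts only with salvage treatment.

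**The effect is small, in a pilot with no test.** This stands. With one or two replaced subjects the shift is 1.4 to 2.7 points, and no decision rule, alpha or power depends on it.

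**Non-completion should be rare, given short courses, the 70% allowance and continuation during Grade III toxicity.** This stands only in part. In Arm B, stopping adjuvant radiation early does not make a subject unevaluable. But the allowance is narrow for short courses, 7.1.1 points both ways, and 11.2.2 does not say whether Arm C's planned radiation includes the adjuvant nodal course.

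**The enrollment mismatch is editorial.** Largely so, because 11.1 and 11.2.2 already settle that recruitment continues until 20 are evaluable.

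Two stronger readings are tempting. A reader might infer that the reported rate will be materially inflated. The documents give neither the number of non-completers nor their response, so the size of any bias is unknown and may be zero. A reader might also infer from 4.2 that enrollment stops at 20, which would raise the maximum interval width to 48.0 points with 18 evaluable or 50.7 with 16. That would mean disregarding the replacement rule in 11.2.2.

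**Conclusion.** The point holds as a gap in the planned analysis that should be closed. Treated subjects who miss the completion rule are removed from the response denominator and replaced, and no all-treated estimate is planned beside a rate meant as a reference. The bias is upward if those subjects respond less often than completers. Its size rests on assumption: 0 to 6.0 points for 0 to 5 replaced subjects with no responses and 6 responders among 20, and none if they respond as often as completers. The pooled shift is small beside the 42.4-point interval. The interval figures in 11.1 are correct. The count of 20 is a matter of wording to reconcile and does not show that the sample size is wrong.

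**What to change.** - In 11.3, keep the evaluable-set rate. Beside it, overall and by arm, report the 6-month PSA response rate with its exact 95% interval in all subjects who start study surgery or study radiation.
- In that second rate, count as non-responders those who do not meet the 11.2.2 rule and those with no 6-month PSA (off study, new anti-cancer therapy, lost to follow-up, or followed for toxicity only).
- Report by arm, with reasons, the number replaced and the number with no 6-month PSA.
- Change 4.2 and the synopsis row for number of subjects to 20 evaluable subjects, with unevaluable subjects replaced, in line with 11.1 and 11.2.2.
- Have the sponsor reconcile the two statements in 7.1.1.

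The cost is one extra table and a few sentences, with no new data. The second rate is a floor: it may be slightly lower, because a non-completer who did respond is counted as a non-responder. It matches a later trial's rate only if that trial uses the same rule. Showing both rates makes this visible.

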11.3 Statistical Hypotheses and Analyses

This study is establishing baseline data for patients who have no defined standard of care therapy. All study data will use descriptive statistics and will be exploratory only.

Since this study is not using any hormonal therapy, we expect that using PSA analysis will be accurate and provide an early readout regarding the potential efficacy and clinical utility of this approach.

Primary Objective

The primary endpoint is the proportion of subjects with a reduction in PSA $\geq 50\%$ 6 months after completion of all treatment (salvage and adjuvant therapy). The observed proportion and a 95% exact binomial confidence interval will be reported for the entire group of evaluable patients (Arms A, B and C together) as well as for each cohort separately.

Secondary Objectives

1. 95% exact confidence intervals will be reported for the observed proportions with reductions in PSA $\geq 50\%$ 12 months after and $\geq 90\%$ 6 and 12 months after completion of all treatment (salvage and adjuvant therapy). This will be done for the entire group of evaluable patients (Arms A, B and C together) as well as for each Arm separately.
2. The proportion of subjects without PSA progression (defined using Prostate Cancer Working Group 3 Criteria PCWG3), will be evaluated every 3 months for 3 years after completion of all treatment (salvage and adjuvant therapy) and analyzed using Kaplan-

Meier methodology. This will be done for the entire group of evaluable patients (Arms A, B and C together) as well as for each Arm separately.

3. The time from study enrollment until the date of confirmed radiographic disease progression as defined by RECIST 1.1 and PCWG3 will be analyzed using Kaplan-Meier methods. This will be done for the entire group of evaluable patients (Arms A, B and C together) as well as for each Arm separately.
4. The time from study enrollment to the initiation of ADT will be analyzed using Kaplan-Meier methods. This will be done for the entire group of evaluable patients (Arms A, B and C together) as well as for each Arm separately.
5. The proportion of patients with a PSA ≤ 0.2 ng/mL will be evaluated 6 and 12 months after completion of all treatment (salvage and adjuvant therapy) in the subset of patients who have previously undergone prostatectomy. This will be done for the entire group of evaluable patients (Arms A, B and C together) as well as for each Arm separately.
6. The number and proportions of subjects with AEs and SAEs as defined by CTCAE version 5.0 will be tabulated both for the entire safety population and also stratified by Arm.
7. 95% confidence intervals will be reported for summary scales of the quality of life (QOL) questionnaires (FACT-P and Expanded Prostate Cancer Index Composite EPIC-26) measured at screening, response assessment visit, and each follow up visit. This will be done for the entire group of evaluable patients (Arms A, B and C combined) and also stratified by Arm. Normal approximations will be used for computation of confidence intervals.

Exploratory Objective

Genomic alterations or abnormal protein expression that correlate with radiation resistance or predilection for early metastasis and worse overall prognosis will be tabulated.

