1.2 Secondary Objectives

1.2.1 To assess additional measurements of response to treatment of oligometastatic disease.

Secondary Endpoints: Proportion of subjects with reductions in PSA $\geq 50\%$ 12 months after and $\geq 90\%$ 6 and 12 months after completion of all treatment (salvage and adjuvant therapy).

1.2.2 To assess PSA progression free-survival following treatment of oligometastatic disease.

Secondary Endpoint: Proportion of subjects without PSA progression (defined using Prostate Cancer Working Group 3 Criteria PCWG3), evaluated every 3 months for 3 years after completion of all treatment (salvage and adjuvant therapy).

1.2.3 To assess time to disease recurrence following treatment of oligometastatic disease.

Secondary Endpoint: The time from study enrollment until the date of confirmed radiographic disease progression as defined by RECIST 1.1 and PCWG3.

1.2.4 To assess time to initiation of ADT for metastatic prostate cancer following treatment of oligometastatic disease.

Secondary Endpoint: The time from study enrollment to the initiation of ADT.

1.2.5 To assess the rate of undetectable PSA following treatment of oligometastatic disease in subjects who have previously undergone prostatectomy.

Secondary Endpoint: In subjects who have previously undergone prostatectomy evaluate the proportion of patients with a PSA ≤ 0.2 ng/mL, evaluated 6 and 12 months after completion of all treatment (salvage and adjuvant therapy).

1.2.6 To assess safety.

Secondary Endpoint: Rate of AEs and SAEs as defined by CTCAE version 5.0.

1.2.7 To assess the impact of study treatment on change in quality of life over three years.

Secondary Endpoint: Quality of life (QOL) questionnaires (FACT-P and Expanded Prostate Cancer Index Composite EPIC-26) will be administered at screening, the Response Assessment Visit, and each follow-up visit.

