6.2.3.3 Subjects whose PSA declines by < 1/3

This will be considered a treatment failure (PSA response failure), no adjuvant therapy will be given. Subjects will enter the follow-up period until diagnosis of metastatic disease and will not receive any further treatment.

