6.4.2 Criteria for the Discontinuation of Study (“Off Study”)

Subjects will be taken off study for the following:

- Study terminated by investigator sponsor
- Completed study follow-up period
- Participant or legally authorized representative requests to be fully withdrawn from the study
- If, in the investigator's opinion, continuation of the trial would be harmful to the subject's well-being.
- Development of an intercurrent illness or situation which would, in the judgment of the investigator, significantly affect assessments of clinical status and trial endpoints.
- Initiation of new anti-cancer therapy
- Subject is lost to follow-up
- Death
- Screen failure

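### The quality-of-life objective is change over three years, but the planned analysis gives only visit-by-visit intervals for scale levels, so within-subject change has no estimate or interval

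*Combined protocol and SAP*

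**What the plan says.** Section 1.2.7 sets the objective: "To assess the impact of study treatment on change in quality of life over three years". The endpoint beneath it says only when FACT-P and EPIC-26 are given: they "will be administered at screening, the Response Assessment Visit, and each follow-up visit". It defines no change measure.

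The analysis is in section 11.3, secondary item 7: "95% confidence intervals will be reported for summary scales of the quality of life (QOL) questionnaires", at those same visits, for all evaluable patients together and by Arm. On method it adds: "Normal approximations will be used for computation of confidence intervals". The opening of section 11.3 sets the general frame: "All study data will use descriptive statistics and will be exploratory only".

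Section 9.3 schedules the questionnaires every 3 months for 3 years after treatment. Three rules elsewhere bear on who is still answering at late visits:

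- Section 6.4.2 takes subjects off study for, among other reasons, "Initiation of new anti-cancer therapy".
- Section 6.2.3.3, for nodal patients whose PSA falls by less than one third, says: "Subjects will enter the follow-up period until diagnosis of metastatic disease and will not receive any further treatment".
- Section 6.4.1, on salvage treatment failure, says: "Patients taken off treatment for treatment failure will continue to be followed for toxicity assessments only every 6 months".

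**The concern.** The objective names one quantity and the analysis estimates another. Carried out exactly as written, item 7 produces a series of intervals for mean score, one per visit, and nothing for how far subjects moved from their own screening value.

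Two things follow for anyone who tries to read change off that series. First, the precision of a change depends on the within-subject correlation between visits, which intervals for separate visits do not show. Second, the difference between two visit means need not track change in individuals if different subjects contribute at the two visits and leaving is related to quality of life. Item 7 does not ask for the number contributing at each visit, so a reader could not see how far the group had altered.

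A smaller, separate matter is the normal approximation. With 20 subjects split over three arms, a fixed 1.96 multiplier applied to an estimated SD gives intervals that are too narrow.

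**Working it through.** **Inputs from the documents.** 20 evaluable subjects (section 11.1); three arms, analysed together and separately (section 11.3); 95% intervals by normal approximation (item 7). Visits: screening, response assessment and 12 quarterly visits over 3 years, giving 14 time points, 13 of them after screening.

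**Inputs assumed.** The documents give no SD, within-subject correlation or drop-out figure for either questionnaire. Results are therefore in SD units, with correlation r from 0 to 0.9 and equal SDs at the two visits.

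**The plan's own precision figures.** The plan states none for quality of life. Those it gives for the primary endpoint reproduce: exact 95% limits are 11.9% to 54.3% for 6/20 and 27.2% to 72.8% for 10/20, a width of 45.6%, which is the maximum.

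**Step 1: a visit mean against a mean change, n = 20.**

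- Half-width of a visit mean = 1.96 × SD/√n = 1.96/√20 = 0.44 SD.
- Half-width of mean paired change = 1.96 × SD × √(2(1 − r)/n).

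| r (assumed) | Half-width for mean change (SD) |
|---|---|
| 0 | 0.62 |
| 0.5 | 0.44 |
| 0.7 | 0.34 |
| 0.9 | 0.20 |

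The same visit intervals of ±0.44 SD are compatible with an interval for change anywhere in this roughly threefold range. The planned output does not say which applies.

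**Step 2: change of contributors (illustration only).** Suppose nobody's score changes, k of 20 subjects have left, and their screening mean was d SD below that of those who stay. The late-visit mean then exceeds the screening mean by (k/20) × d. With d = 0.5:

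| Left (k) | Shift (SD) | Subjects remaining | 1.96 half-width of late-visit mean (SD) |
|---|---|---|---|
| 4 | 0.10 | 16 | 0.49 |
| 6 | 0.15 | 14 | 0.52 |
| 10 | 0.25 | 10 | 0.62 |

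Both k and d are invented for the illustration. Each shift lies well inside the interval for the late-visit mean.

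**Step 3: coverage of the normal approximation.** This assumes that the approximation means 1.96 with the sample SD and that scores are normal. Coverage = 2 × F(1.96; n − 1) − 1, where F is the t distribution function: 93.5% at n = 20, 92.8% at 14, 91.8% at 10 and 89.3% at 6. Coverage falls as n falls. The smallest of three arms sharing 20 subjects has at most 20/3, rounded down, which is 6. At least one by-Arm set of intervals therefore covers at most 89.3%, even with every questionnaire returned.

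**The case against.** The strongest reply is that item 7 does what the endpoint asks. The endpoint under 1.2.7 is questionnaire administration at stated visits, item 7 summarises exactly those visits, and everything is declared descriptive. Individual scores are collected, so change can be computed later with nothing lost. This lowers the weight of the point but does not remove it. A mean change with an interval is itself a descriptive statistic, and it is the one that the objective names. Leaving it to the analyst means choosing scores and visits, among 13 after screening, once the data are seen.

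Some stronger readings are tempting and should be resisted.

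- *Visit means are comparable only if the same subjects contribute.* Too absolute. They are also comparable if leaving is unrelated to quality of life, or under a suitable longitudinal model. The plan states neither, but neither is ruled out.
- *The plan's intervals for change are too wide.* A reader who treated visits as independent would get an interval √2/√(2(1 − r)) times the paired width, or 1.41, 1.83 or 3.16 times at r = 0.5, 0.7 or 0.9. Item 7 plans no such interval, so that would be the reader's error.
- *Drop-out will bias the late visits.* No section says that leavers have poorer screening scores. The shifts in step 2 are hypothetical and small beside the sampling error.
- *Three separate rules remove subjects from questionnaire follow-up.* Only new anti-cancer therapy (6.4.2) is a clear exit. Section 6.2.3.3 ends follow-up at diagnosis of metastatic disease, yet inclusion criterion 5.1.5 already defines every subject by metastatic lesions, so that end point is undefined. Section 6.4.1 is an off-treatment rule. The calendar footnotes first recommend restaging CT 6 months after all treatment, so it is unclear whether the rule covers progression found after treatment is complete.

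**Conclusion.** The point holds as a mismatch between objective and analysis: followed exactly, the plan produces no estimate or interval for within-subject change, and none can be recovered from what it does produce. The 0.62 to 0.20 SD range rests on assumed correlations and equal SDs. That the interval is undetermined without the correlation does not depend on the values chosen.

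The coverage shortfall is conditional on the 1.96 reading, which the text does not spell out, and on normal scores. It is slight for the pooled group (93.5%) and material only by Arm (at most 89.3% in the smallest). Drop-out is a reason to report who contributes at each visit; the documents do not show that late-visit means will in fact be biased.

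This should be corrected, but its severity is modest. The endpoint is secondary and descriptive, and the primary endpoint, the sample size and data collection are untouched.

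**What to change.** Reword item 7 along these lines: *For each FACT-P and EPIC-26 summary score, the mean within-subject change from screening, its t-based 95% confidence interval and the number of subjects contributing will be reported at the response assessment visit and at each follow-up visit, for all evaluable patients and by Arm. Any visit means also shown will carry t-based intervals. Results at late visits apply to subjects still in follow-up.*

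Listing the summary scores, naming the visits to be emphasised and stating how incomplete questionnaires are handled would be useful, but these are details at the authors' discretion. The authors should also clarify how the follow-up rules in sections 6.2.3.3 and 6.4.1 fit with the three-year questionnaire schedule in section 9.3, since that determines who can contribute.

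No new data are needed. The cost is a reworded paragraph and wider intervals in small groups: the t multiplier is 2.093/1.96 = 1.07 times the normal one at n = 20 and 2.571/1.96 = 1.31 times at n = 6. Two limits remain. The t interval is still approximate for bounded, skewed scores in very small arms. Pairing removes the artefact of comparing different sets of subjects, but it does not make those who remain representative of those who left.
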